2.3.2. Benefit Assessment

Benefits to individual subjects may include access to medical evaluations/assessments associated with study procedures (eg, physical examinations, ECGs, laboratory evaluations, SARS-CoV-2 [severe acute respiratory syndrome coronavirus 2; COVID-19] diagnostic testing).

2.3.3. Overall Benefit: Risk Conclusion

Taking into account the measures taken to minimize risk to subjects participating in this study, the potential risks identified in association with IW-3300 are justified by the anticipated benefits to patients with IC/BPS.

3. OBJECTIVES AND ENDPOINTS

3.1. Objectives

3.1.1. Primary Objective

To assess the safety and tolerability of 7-day dosing with multiple-ascending doses of IW-3300 administered rectally via enema in healthy subjects

3.1.2. Exploratory Objectives

The exploratory objectives are:

- To summarize the PK of 7-day dosing with IW-3300 administered rectally via enema in healthy subjects
- To explore potential changes to the microbiome with 7-day dosing with IW-3300 administered rectally via enema in healthy subjects

3.2. Estimands

Not applicable for this Phase 1 study

3.3. Endpoints

3.3.1. Primary Endpoints (Safety)

The primary endpoints are:

- Incidence of TEAEs
- Incidence of TESAEs

3.3.2. Exploratory Endpoints

The exploratory endpoints are:

- PK parameters (IW-3300 and metabolites in plasma)
- Change in 16s RNA based analysis of gut microbiome composition at the genus level from baseline to 7 days post IW-3300 administration

4. STUDY DESIGN

4.1. Overall Design

This is a Phase 1, single-center, randomized, double-blind, placebo-controlled, multiple-ascending-dose study of IW-3300 administered rectally, once-daily, for 7 days as a low-volume enema in healthy adult subjects. This study will assess the effect of IW-3300 on safety, tolerability, and PK, and also explore the potential effect of IW-3300 on gut microbiome composition.

Subjects in each dosing cohort will progress through 3 study periods: (1) Screening Period, (2) Clinic Period, and (3) Follow-up Period; these periods and the progression between cohorts are illustrated in the study schematic ([Figure 1](#)). Treatment duration will be 7 days; subjects will be followed in the Phase 1 clinical research unit (CRU) for the duration of dosing, until at least 24 hours after the last dose of study drug and contacted by phone for follow-up approximately 14 days after the last dose. Total subject participation will be 29 to 57 days, including the Screening, Clinic, and Follow-up Periods.

The study will evaluate multiple-ascending doses of IW-3300 in a double-blind manner. The 9 subjects within each cohort will be randomized to receive IW-3300 (6 subjects) or placebo (3 subjects), administered rectally, once-daily for 7 days (as a low-volume [20 mL] enema) following a fast of at least 6 hours (refer to the SoA [[Table 1](#)] for additional details regarding dosing instructions). The planned cohorts are:

- Cohort 1: IW-3300 100 µg or matching placebo rectal dose once daily
- Cohort 2: IW-3300 300 µg or matching placebo rectal dose once daily
- Cohort 3 (optional): IW-3300 >100 µg but <300 µg or matching placebo rectal dose once daily (decision to enroll this cohort will be determined after safety reviews of previous cohorts, in the case of intolerance at 300 µg but tolerability at 100 µg)

A Dose Escalation Committee will conduct blinded reviews of all the safety/tolerability parameters of the IW-3300 100-µg dosing cohort through Discharge (Day 8) in order to make a decision regarding dose escalation to the next IW-3300 dosing cohort. The Dose Escalation Committee will include sponsor and contract research organization (CRO) representatives. Dose escalation is detailed in Section [6.6](#).

4.1.1. Study Periods

4.1.1.1. Screening Period

The Screening Period will begin with the signature of the informed consent form (ICF) at the Screening Visit (which can occur from Day -36 to Day -8) and will last 7 to 35 days. At the Screening Visit, subjects will undergo preliminary screening procedures to ensure that they meet the inclusion and exclusion criteria for the study. Eligible subjects will receive the BM portion of the bladder and bowel movement diary (BBMD), a paper-based diary to complete on an event-driven basis (ie, for each BM) at home, and training on how to complete it to record their bowel habits. Subjects will complete the BM portion of the BBMD daily only for the 7 days before

Check-in on Day -1. The end of the Screening Period will coincide with the beginning of the Clinic Period at Check-in (Day -1).

4.1.1.2. Clinic Period

The Clinic Period will begin at Check-in to the Phase 1 CRU on Day -1 (the day before dosing), and will end at the time of Discharge on Day 8 (the day after dosing). Following confirmation of eligibility at Check-in, subjects will be admitted to the CRU and will undergo baseline procedures. On the morning of Day 1 (note that there is no Day 0), subjects in each cohort will undergo predose assessments and will be randomized in a 2:1 ratio to receive IW-3300 or matching placebo after a fast of at least 6 hours.

The assessments conducted during the Clinic Period are shown in the SOA ([Table 1](#)). Daily safety assessments will be performed. Subjects will continue to enter their BM information into the BBMD on an event-driven basis. The questions related to bladder/urinary symptoms in the BBMD will be collected predose on each dosing day, with a 24-hour recall period at each timepoint to ascertain any undesirable effects on the bladder or potential urinary symptoms. Blood samples for PK assessments will be collected at specified times predose (blood) and postdose (blood and stool). Subjects will be confined to the CRU from Check-in (Day -1) through Discharge (Day 8), which will occur after completion of the assessments (at least 24 hours after the last administration of study drug) and at the investigator's discretion.

4.1.1.3. Follow-up Period

The Follow-up Period will start immediately after subjects are discharged from the Phase 1 CRU on Day 8 and will last until Day 21 (+3). On Day 21 (+3), the Phase 1 CRU will contact subjects for the Follow-up Phone Call (at the discretion of the investigator, subjects may be requested to return to the Phase 1 CRU for their follow-up contact). The Follow-up Phone Call will be considered the end of the study for that subject.

4.2. Scientific Rationale for Study Design

A randomized, double-blind, placebo-controlled study design was chosen to investigate the effects of IW-3300 administered once daily for 7 days as a low-volume enema. Subjects will be randomized within each cohort to ensure that the treatment groups are comparable and to minimize the potential for selection bias. The study will be double-blind to ensure that the subjects and CRU staff are unaware of the treatment assignment and to minimize the potential for bias in study assessments or AE reporting. Placebo was chosen as the control so that the rate of spontaneously occurring AEs can be determined and to reduce the potential for bias in the reporting of AEs.

To ensure a thorough assessment of safety, subjects will be confined to the CRU for the duration of the Clinic Period, from Check-in (Day -1) through until Discharge (Day 8), which will occur after completion of the assessments (at least 24 hours after administration of study drug) and at the investigator's discretion. CRU staff will contact subjects for the Follow-up Phone Call on Day 21 (+3), conducted 14 days after the last dose, for safety follow-up; at the discretion of the investigator, subjects may be requested to return to the CRU for their follow-up contact.

To evaluate any effects of IW-3300 on bowel and bladder function, subjects will complete the BM portion of the BBMD on 7 consecutive days during the Screening Period to establish a

baseline for bowel function without study drug. Similarly, subjects will provide answers to the bladder/urinary-symptom-related questions in the BBMD predose on Day 1, with a 24-hour recall, to establish a baseline without study drug.

Because this is the first multiple-dose study with IW-3300 in humans, cohorts will be enrolled sequentially, following a safety review of prior dosed cohort(s) by a Dose Escalation Committee (Section 6.6). In addition, stopping criteria have been established to ensure that dosing at the same or higher dose levels will stop should a safety signal be detected (Section 7.1.1). In this case, a lower dose of IW-3300 could be used.

4.2.1. Subject Input into Design

There was no subject involvement in the design of this clinical study.

4.3. Justification for Dose

This study is intended to evaluate the effects of multiple doses of IW-3300 when administered rectally as a low-volume (20 mL) enema. This route of administration was selected to target effects of IW-3300 to the colon. The nonclinical toxicology data support the proposed IW-3300 Phase 1 starting dose of 100 µg/subject/day with an approximate 240-fold safety factor compared to the nonclinical NOAEL, resulting in the lowest HED. The 100 µg and 300 µg doses were also selected based on nonclinical pharmacology models of visceral hypersensitivity and bladder dysfunction using IW-3300.

[REDACTED] The highest dose level evaluated in this study will be 300 µg, which is approximately 80-fold lower than the HED based on body weight conversion of the lowest NOAEL (24,000 µg) identified in nonclinical toxicology studies.

4.4. End of Study Definition

A subject is considered to have completed the study if he/she has completed all phases of the study including the Follow-up Phone Call.

The end of the study is defined as the date of the last Follow-up Phone Call of the last subject in the study.

5. STUDY POPULATION

Prospective approval of protocol deviations to recruitment and enrollment criteria, also known as protocol waivers or exemptions, is not permitted.

5.1. Inclusion Criteria

Subjects are eligible to be included in the study only if all of the following criteria apply:

Age

1. Subject is 18 to 60 years of age, inclusive, at the time of signing the ICF.

Type of Subject and Disease Characteristics

2. Subject is medically healthy with no clinically significant findings during medical evaluation including physical examination, 12-lead ECG, and clinical laboratory tests (serum chemistry, hematology, urinalysis, and urine drug and alcohol screen). (NOTE: In making this determination, the investigator or designee will consider whether any finding could prevent the subject from performing any of the protocol-specified assessments, could represent a condition that would exclude the subject from the study, could represent a safety concern if the subject participates in the study, or could confound the study-specified assessments [eg, incontinence, overactive bladder, prostatitis, urinary tract infection]).
3. Subject has normal formed bowel movements (≥ 3 per week and ≤ 3 per day; average BSFS score of >2 and <6 , as reported in the BBMD during the 7 days before Check-in [Day -1]).
4. Subject agrees to refrain from making any new or major lifestyle changes (eg, new diet or exercise regimen) from the Screening Visit until after the Follow-up Phone Call on Day 21.
5. If subject is ≥ 45 years of age, subject is compliant with colorectal cancer screening guidelines according to the American College of Gastroenterology (ACG) Clinical Guidelines: Colorectal Cancer Screening 2021. (8)

Weight

6. Subject's body mass index (BMI) is within the range 18.5 to 35.0 kg/m² (inclusive) at the Screening Visit.

Sex

7. Male and female subjects
 - a. Female subject is of nonchildbearing potential (ie, women who are postmenopausal [greater than 12 months without menses] or who have had a procedure such as a bilateral oophorectomy, bilateral salpingectomy, or hysterectomy).
 - b. Subject is willing to abstain from sexual intercourse during the period of confinement in the CRU.

- c. Male subject and female partner(s) are willing to use a double-barrier method of contraception during the study (eg, diaphragm with spermicide plus a condom, condom with spermicide plus a diaphragm or cervical cap), from the Screening Visit until after the Follow-up Phone Call on Day 21.

Informed Consent

8. Subject is capable of giving signed informed consent as described in Appendix 1/ Section 10.1, which includes compliance with the requirements and restrictions listed in the ICF and in this protocol.

5.2. Exclusion Criteria

Subjects are excluded from the study if any of the following criteria apply:

Medical Conditions

1. Subject has evidence or history of clinically significant acute or chronic disease, or clinically significant illness within 30 days of the Screening Visit.
2. Subject has a history of clinically significant hypersensitivity or allergies to any of the inactive ingredients contained in the active or placebo drug products.
3. Subject has a history of any condition that would interfere with their ability to receive an enema.
4. Subject has a recent history of anal fissure, anal abscess, complicated hemorrhoids, active proctitis, or presence or history of ulcerative colitis or Crohn's disease.

Prior/Concomitant Therapy

5. Subject has used a prescription medication during the 14 days before Check-in (Day -1). Use of prescription medication, unless necessary to treat a medical emergency, is excluded during the study until after the Follow-up Phone Call on Day 21.
6. Subject has used any over-the-counter medications, including laxatives, during the 7 days before Check-in (Day -1). Use of over-the-counter medication, including laxatives, is not permitted during the study until after Discharge on Day 8. (Note: Acetaminophen may be used at the investigator's discretion, in consultation with the sponsor, as per Section 6.5.)
7. Subject has used vitamins, dietary, or herbal supplements from 7 days before Check-in (Day -1). Use of these supplements is not permitted during the study until after Discharge on Day 8.
8. Subject has received a licensed vaccine during the 14 days before Check-in (Day -1) or is planning to receive any vaccine during the study (up to the Follow-up Phone Call on Day 21).
9. Subject has received blood products during the 2 months before Check-in (Day -1).
10. Subject has undergone a surgical procedure during the 30 days before Check-in (Day -1), other than minor dermatologic procedures, or has a history of any surgery involving the

GI tract or anal canal (with the exception of endoscopic procedures, appendectomy, and cholecystectomy).

Prior/Concurrent Clinical Study Experience

11. Subject has received any investigational drug or vaccine during the 30 days or 5 half-lives of that investigational drug (whichever is longer) before the Screening Visit, or is planning to receive another investigational drug at any time during the study (up to the Follow-up Phone Call on Day 21).

Diagnostic Assessments

12. Subject has a 12-lead ECG demonstrating severe bradycardia (heart rate <40 beats per minute) or average QTcF \geq 450 msec for males and \geq 470 msec for females at the Screening Visit or at Check-in on Day -1.
13. Subject has elevated (>1.5 times the upper limit of normal as defined by the laboratory) levels of alanine aminotransferase (ALT), aspartate aminotransferase (AST), creatinine, or bilirubin at the Screening Visit or at Check-in on Day -1.
14. Subject has confirmed or suspected infection with SARS-CoV-2 (COVID-19) at the Screening Visit or Check-in on Day -1, or was diagnosed with COVID-19 or had contact with a person with COVID-19 within 14 days of the Screening Visit.
15. Subject has positive serology for human immunodeficiency virus (HIV)-1, HIV-2, or hepatitis B surface antigen (HBsAg), or positive for anti-HIV-1, anti-HIV-2, or anti-hepatitis C virus (HCV) antibodies at the Screening Visit.
16. Identification of an anatomical abnormality upon Screening rectal examination which will make enema administration difficult.

Other Exclusions

17. Subject has a history of difficulty receiving an enema.
18. Subject has a history of alcohol or drug addiction during the year before the Screening Visit, or has a positive drug or alcohol screen at the Screening Visit or Check-in on Day -1.
19. Subject has ingested any alcohol-containing foods or beverages during the 48 hours before Check-in (Day -1). Ingestion of alcohol-containing foods or beverages is excluded during the study until after the Follow-up Phone Call on Day 21.
20. Subject has donated blood products during the 6 weeks before Check-in (Day -1).
21. Subject is involved in the conduct and administration of this study as an investigator, subinvestigator, study coordinator, other study staff, or sponsor staff.

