^f For orthostatic blood pressure and pulse measurements, the subject must lie quietly for ≥ 5 minutes before supine/semisupine blood pressure and pulse measurements are taken, then assume standing position for 3 minutes before standing blood pressure and pulse measurements are taken. If a subject has orthostatic symptoms upon standing (eg, palpitation, dizziness), they will be assisted and asked to lie down without waiting the 3 minutes for vital sign assessment. Orthostatic measurements may be taken at other vital signs collection timepoints if clinically indicated, at the discretion of the investigator. When applicable, vital sign measurements will be obtained before blood draws.

^g ECGs should be obtained after the subject has been supine for at least 5 minutes. At each timepoint required, 3 individual ECG tracings should be obtained as closely as possible in succession, but no more than 2 minutes apart. The full set of triplicates should be completed in less than 4 minutes.

^h Elevated inflammatory markers (ESR, CRP), and/or relevant symptoms (eg, rectal pain, hematochezia) may be suggestive of colonic inflammation; subjects with these signs or symptoms should undergo recto-sigmoidoscopy. If this is negative, a colonoscopy may be performed after a discussion between the investigator and the Sponsor.

ⁱ HCG at Screening will be a blood-based test. HCG at Check-in/Day -1 will be a urine-based test.

^j The BM portion of the BBMD will be completed by the subject on an event-driven basis. For subjects with Screening Visits earlier than Day -9, CRU staff will call subjects on Day -9 to remind them to begin recording their BMs in the BBMD the following day, answer any questions, and provide additional BM pages via email, if needed. Bladder information in the BBMD will be collected predose on each dosing day, with a 24-hour recall period at each timepoint.

^k CRU staff will review the subject's Screening Period BBMD at Check-in to confirm that subjects have at least 3 bowel movements during the 7 days prior to Check-in (Days -8 through -2) and no more than 3 bowel movements per day to be eligible for the study; CRU staff will collect the subject's Clinic Period BBMD at Discharge.

^l Subjects will remain at the CRU from Check-in (Day -1) through Discharge (Day 8).

^m Subjects will fast for at least 6 hours prior to dosing on Days 1 through 7 and for at least 1 hour following dosing. During these times, water is permitted.

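### Exclusion criterion 14 counts its 14-day COVID-19 diagnosis/contact look-back from Screening only, so a known contact shortly before Check-in is not clearly excluded

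*Protocol*

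**What the plan says.** Criterion 14 in Protocol Section 5.2 has two limbs with different anchors.

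- **Current infection** is tied to both visits: "Subject has confirmed or suspected infection with SARS-CoV-2 (COVID-19) at the Screening Visit or Check-in on Day -1".
- **Recent diagnosis or contact** is tied to one visit: the subject "was diagnosed with COVID-19 or had contact with a person with COVID-19 within 14 days of the Screening Visit".

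Section 4.1.1.1 gives the timing of the Screening Visit and the length of the period it opens: "which can occur from Day -36 to Day -8) and will last 7 to 35 days".

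Two other 14-day look-backs in Section 5.2 count from Check-in. Criterion 5 reads "Subject has used a prescription medication during the 14 days before Check-in (Day -1" and criterion 8 reads "Subject has received a licensed vaccine during the 14 days before Check-in (Day -1". Over-the-counter drugs and supplements (7 days, criteria 6 and 7) and alcohol intake (48 hours, criterion 19) count from Check-in too.

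The Schedule of Activities repeats the eligibility review and the SARS-CoV-2 test at Check-in and schedules no later test. ESR and CRP are drawn at Check-in and at Discharge. Footnote h says of them: "Elevated inflammatory markers (ESR, CRP), and/or relevant symptoms (eg, rectal pain, hematochezia) may be suggestive of colonic inflammation". It then directs subjects with such findings to recto-sigmoidoscopy.

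**The concern.** A look-back on contact is useful if it reaches the days just before a subject enters the unit. Counted from Screening, it can end weeks before entry. Repeating the eligibility review at Check-in does not cure this, because the rule being re-checked still points to the Screening Visit. A subject screened on Day -36 with a known contact on Day -3, no symptoms and a negative test on Day -1 falls outside the contact limb on either reading of the window. That subject is excluded only if the investigator stretches the undefined term for suspected infection.

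The stake is twofold. The subject, and possibly others in the unit, would be exposed to an avoidable illness during confinement. The safety data would also be less clean: an infection that surfaces after the first dose can produce treatment-emergent events, and it may raise the Day 8 ESR or CRP, which the plan treats as possible signs of colonic inflammation.

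**Working it through.** **Inputs (all from the Protocol)**

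- Screening Visit on Day S, with S from -36 to -8: 29 permitted dates (Section 4.1.1.1).
- Check-in on Day -1 and first dose on Day 1; Section 4.1.1.2 adds "note that there is no Day 0".
- Confinement, Schedule of Activities footnote l: "Subjects will remain at the CRU from Check-in (Day -1) through Discharge (Day 8").
- Look-back of 14 days from Screening (criterion 14).
- Six active and three placebo subjects per cohort, with two cohorts and an optional third (Section 4.1).

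**Reproducing the plan's own figures**

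- Screening length = (-1) - S. For S = -8 this is 7 days; for S = -36 it is 35 days. The stated range is 7 to 35 days.
- Total participation = |S| + 21. This gives 8 + 21 = 29 and 36 + 21 = 57 days. The stated range is 29 to 57 days.

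The day arithmetic therefore agrees with the documents.

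**Coverage of the 14 days before Check-in (Days -15 to -2)**

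Write the Screening Visit as Day -s, with s from 8 to 36.

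*Backward reading* (window from Day -s-14 to Day -s): days covered = 16 - s for s = 8 to 15, and 0 for s of 16 or more.

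| Screening on | Dates | Days covered, of 14 |
|---|---|---|
| Day -8 to Day -15 | 8 | 8 falling to 1 |
| Day -16 to Day -36 | 21 | 0 |

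- No date has full coverage, and 21/29 = 72% have none.
- Mean coverage over the permitted dates is (8+7+6+5+4+3+2+1)/(29 × 14) = 36/406 = 8.9%.
- The days from just after Screening to Day -2 number s - 2, so 6 to 34 days, and are never covered.

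*Two-way reading* (window from Day -s-14 to Day -s+14): days covered = 14 for s up to 16, 30 - s for s = 17 to 29, and 0 for s of 30 or more.

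| Screening on | Dates | Days covered, of 14 |
|---|---|---|
| Day -8 to Day -16 | 9 | 14 |
| Day -17 to Day -29 | 13 | 13 falling to 1 |
| Day -30 to Day -36 | 7 | 0 |

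- At least one day is uncovered for 13 + 7 = 20 of 29 dates (69%).

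*Sensitivity to the 14 days.* The documents give no incubation period, so the reference window is the protocol's own 14 days. If the relevant window before Check-in is assumed to be 10, 7 or 5 days, the backward reading covers none of it for 25, 28 and 29 of the 29 dates.

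*With a Check-in anchor*, all 14 days are covered for all 29 dates.

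**Size in the safety tables, if one extra subject has a treatment-emergent event**

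- Dose group: 1/6 = 17 percentage points.
- Pooled placebo: 1/6 = 17 points with two cohorts, 1/9 = 11 points with three.

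**The case against.** The strongest reply is that the gap is already narrowed. Check-in includes a SARS-CoV-2 test, a complete physical examination, oral temperature and an exclusion for suspected infection. Inclusion criterion 2 lets the investigator weigh findings that raise a safety concern or could confound assessments, and Section 10.2 allows extra tests at any time. ESR and CRP are drawn at Check-in, so a rise already present at entry shows at baseline. All of this stands, and it lowers the risk. It still leaves the asymptomatic, test-negative contact to the investigator's reading of an undefined term.

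A second reply is that a Screening anchor is not unique. Criterion 1 (recent illness) and criterion 11 (investigational drugs) also count from Screening. That is correct, so it cannot be said that every other look-back runs from Check-in. The contrast holds for look-backs of 14 days or less. Those comparators are mainly medication washouts, and the documents give no reason for the different anchor.

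A reader might also infer larger consequences that the documents do not support:

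- **That the whole confinement period is the treatment-emergent window.** Under Protocol Section 10.3.1.2 and SAP Section 7.1, such events start or worsen only after the first dose on Day 1. Illness evident before then is pretreatment.
- **That one case moves placebo incidence by 33 points.** This holds only for a single cohort's three placebo subjects. Protocol Section 9.4.1 and SAP Sections 6 and 7 provide for pooling placebo across cohorts where appropriate.
- **That an infection would by itself trigger suspension or distort escalation.** Every suspension trigger in Section 7.1.1 requires an event judged related to study drug, Section 10.3.3.3 requires alternative causes to be considered, and the committee reviews all the safety data.
- **That infection would spread through a nine-subject cohort.** Day numbers are relative to each subject, and the documents do not say that all nine are confined at the same time.

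**Conclusion.** The point holds as a gap in an eligibility rule. On the backward reading, the diagnosis/contact limb misses the whole 14 days before Check-in for 21 of 29 permitted screening dates. On the reading kindest to the plan, 20 of 29 dates are incompletely covered. A recent known contact without symptoms and with a negative Check-in test is not clearly excluded.

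The possible effect on the data is one extra subject with a treatment-emergent event (17 points in a dose group; 17 or 11 points in pooled placebo), plus a Day 8 ESR or CRP rise unrelated to the colon. The points figures assume that the infection produces an event in a subject who would otherwise have had none.

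The coverage counts weight all permitted screening dates equally. The actual distribution of those dates and the probability of exposure are not given, so the frequency is unknown. No sample size, power or error rate is affected, since no hypothesis test is planned. This is a worthwhile low-cost improvement and does not threaten the study's conclusions.

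**What to change.** Amend the history limb of criterion 14 so that diagnosis or contact excludes if it fell within 14 days before the Screening Visit or within 14 days before Check-in (Day -1). This matches the two-visit form of the criterion's infection limb and the Check-in anchor of criteria 5 and 8. Stating the direction of the window also removes the backward versus two-way ambiguity. Add the contact question to the existing Check-in eligibility review. If the Screening-only anchor is deliberate, state the reason.

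The cost is one phrase in an amendment, one question at a visit that already takes place, and an occasional extra exclusion at Check-in.
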